A version of the statistical model above was fit to 79 weeks of preliminary baseline data (i.e., with no intervention effect X_{kt}) in order to estimate the parameters (e.g., $\boldsymbol{\nu}_A, \boldsymbol{\Sigma}_A$) needed to simulate longitudinal data for the 15 clusters. Clusters were randomly allocated to the steps in **Figure 1**, and treatment effects due to intervention were generated on a grid of eight values $\nu_{1B} = 0.00, 0.01, 0.02, 0.03, 0.05, 0.10, 0.15, 0.20$, with the remaining $\nu_{2B} = \nu_{3B} = \nu_{4B} = \nu_{5B} = 0$ to assume the most conservative case (i.e., only a single symptom is affected by the intervention). The cluster effects were then generated according to $\boldsymbol{B}_k \sim N(\boldsymbol{\nu}_B, \sqrt{\nu_{1B}} \boldsymbol{\Sigma}_A)$. This data generation process was used to simulate 100 data sets under each of the eight grid values for ν_{1B} . The full model above was then used to estimate $\boldsymbol{\nu}_B$ and test the hypothesis that all $\nu_{jB} = 0$, via simultaneous credible bounds.⁹⁷ The results are provided in **Figure 3**. As can be seen in the figure, the test keeps very close to the nominal level (i.e., 0.01, 0.05, or 0.10, respectively) when there is no effect. However, the power rises quickly to detect even a small average score difference of even 0.10 with 70% power (at 0.05 LOS) and a difference of 0.20 with nearly 100% power.

Data Analysis Plan:

Specific Aim 1 Analyses.

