To test the primary hypothesis H1a for our primary outcomes, we will use generalized linear mixed models to assess the effects of the intervention on each of the 6 SPPADE scores⁹⁰. All models will account for correlation of outcomes within clusters and across patients, and for changes in this correlation over time. We will adjust for time, measured by study period, to account for temporal effects. Each score will be adjusted for the prior score, with a coefficient that depends on the time t since the prior score; to account for potential changes in correlation of outcomes by over time we will include autoregressive terms at the patient level.⁹¹ To account for changing correlation within clusters over time we will incorporate a discrete-time correlation structure.⁹⁸

Our primary analysis will treat each SPPADE score as a continuous variable and employ a mixed effects generalized multivariate model; we will model all 6 scores jointly, which will allow us to account for the correlation between them and avoid correcting for multiple hypothesis tests.

Specifically, let Y_{ijkm} be the i^{th} score ($i=1,\dots,6$) of the j^{th} encounter for the k^{th} patient in the m^{th} cluster ($m=1,\dots,15$), for $j = 2,\dots$; the first score for each patient ($j=1$) is a baseline score collected during the first visit, not an outcome. Let $w=1,\dots,6$ indicate the trial step during which the survey is collected.

Then to test the hypothesis that the intervention impacts the 6 symptom scores we will estimate the joint models:

$$Y_{ijkm} = A_{ikm} + \mathbf{B}_i X_{jkm} + \mathbf{L}_i(t) Y_{i[j-1]km} + \mathbf{F} \mathbf{Z}_k + \mathbf{D} \mathbf{S}_m + \mathbf{Q} q_{jmk} + \mu_{imw} + \nu_{it} \quad ; \quad i=1,\dots,6 \quad (1)$$

where

X_{jkm} is an intervention indicator which equals 1 if encounter j for patient k in cluster m was post intervention and 0 otherwise;

\mathbf{B}_i is a vector of fixed effects for the intervention on symptom score i , $i = 1,\dots,6$;

\mathbf{L}_i is a vector of time dependent lags, representing the effect of the most recent measurement on the current one, as a function of time t in days between measures;

\mathbf{Z}_k is a vector of patient factors for patient k , \mathbf{F} is a corresponding vector of fixed effects;

\mathbf{S}_m is a cluster level set of indicators for randomization strata, \mathbf{D} is a vector of fixed effects;

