\mathbf{Q} is a vector representing the secular time effect, where q_{jmk} is the calendar quarter; and, the time elapsed since encounter $j-1$; for $j=2,\dots$

In addition

A_{ikm} is a vector of random effects, $[A_{1km},\dots,A_{5km}]$ specified as varying across patients nested within clusters

$$A_{ikm} \sim [A_i + \alpha_{ikm} + \gamma_{im}]; \quad i=1,\dots,6$$

$$[\alpha_{ikm}] \sim N(0, \Sigma_\alpha)$$

$$[\gamma_{im}] \sim N(0, \Sigma_\gamma)$$

where Σ s are exchangeable correlation matrices.

μ_{imw} , $i=1,\dots,6$ is a discrete-time vector of random effects for each cluster m and step w ; and,

ν_{it} , $i=1,\dots,6$ is a multivariate autoregressive process of order 1, AR(1) with Gaussian noise, to account for time dependent correlation of responses within each patient over time; and,

Prior to estimating this model, the distributions of the SPPADE scores will be examined and, if appropriate, transformed to have approximately normal distributions. Covariates will be similarly reviewed and either transformed or categorized before inclusion in the model.

In general, fitting the above models (1) which has several random effects (in both time and across clusters) can be challenging. However, Markov Chain Monte Carlo estimation is very effective at fitting such models and are appropriate for assessing stepped-wedge cluster randomized designs.⁹⁹ Moreover, by incorporating historical time trends into our priors for the effect of calendar time, a Bayesian model can increase statistical power relative to a frequentist approach.¹⁰⁰ All other priors will be flat. In the event that model (1) can't be estimated, we will simplify the error structure and other features using review of variable distributions and correlations, including intra-cluster correlations and time dependent correlation, to inform the simplifications. Then, using our final model we will calculate posterior probabilities and credible intervals to assess whether coefficients differ from zero; specifically, we will achieve the primary aim of the study by calculating the posterior probabilities that each of B_1, \dots, B_6 is greater than 0; we will accept that the intervention is effective if $PP[\text{abs}(B_i) > 0, i=1,\dots,6] \geq 0.80$.

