$$Y_{ijkm} = A_{ikm} + B_i X_{jkm} + C E_{ijkm} + D_i E_{ijkm} X_{jkm} + L_i(t) Y_{i[j-1]km} + F Z_k + D S_m + Q q_{jmk} + \mu_{imw} + \nu_{it} \quad ; \quad i=1, \dots, 6 \quad (2)$$

We will then test the hypothesis as above by calculating the $PP[\text{Abs}(D_i) > 0, i=1, \dots, 6]$

In the event that the model with patient surveys as the unit of analysis cannot be computed to test Hypotheses H1b, we will use the cluster-period approach outlined for testing H1a, but will summarize SPPADE NRS scores for each cluster-period according to whether the patient had any prior elevated scores; we will then estimate a model analogous to the cluster-period model used to test Hypothesis H1a but including an indicator for post-elevation and the interaction with the intervention indicator.

Finally, as a secondary objective of this aim, to better understand the effectiveness of different components of the E2C2 intervention in reducing symptoms, we will perform a separate set of analyses to assess the impact of specific process measures (D.2.d) on SPPADE scores and other clinical outcomes. For each process measure we will first examine the distribution of values (frequency or duration) and, if highly skewed, categorize into 2 or more categories. We will then estimate for each outcome a mixed effects linear model with a random cluster effect, where the outcome is the dependent variable and the main independent variable is the continuous or categorized process measure, adjusting for patient covariates as described above. By testing for an overall process measure effect, we can assess which processes contribute most to reducing outcomes; we will also report measures of variance explained to enable relative comparison of process measure effects.

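### The stated power and error rates describe a simultaneous-bounds test of five effects, not the posterior-probability rule that will decide H1a

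*Combined protocol and SAP*

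**What the plan says.** Under Power Statement, treatment effects were simulated for five scores, with one non-zero effect and the other four set to zero. Each of eight effect sizes had 100 simulated data sets. The hypothesis that all five effects are zero was tested "via simultaneous credible bounds". The section reports error close to nominal at 0.01, 0.05 and 0.10, then that "the power rises quickly to detect even a small average score difference of even 0.10 with 70% power" at the 0.05 level, and nearly 100% power at 0.20.

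Under Hypotheses H1a, six scores are modelled jointly, which is said to "account for the correlation between them and avoid correcting for multiple hypothesis tests". The plan will compute the posterior probability that each of B_1 to B_6 "is greater than 0; we will accept that the intervention is effective if" PP[|B_i| > 0, i = 1 to 6] ≥ 0.80. Apart from the calendar-time effect, which has an informative prior, "All other priors will be flat".

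Under Hypotheses H1b: "We will then test the hypothesis as above by calculating the" same kind of probability for the interaction coefficients D_i. No threshold is repeated there, and no power is given.

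**The concern.** A power calculation supports a design only if it uses the rule that will decide the trial. Here the two rules differ in form (simultaneous bounds against a posterior probability), in threshold (0.05 against 0.80) and in number of outcomes (five against six). Nothing in the documents connects them.

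The planned rule also has a problem of its own. A continuous posterior puts no mass at exactly zero, so |B_i| > 0 has probability 1 and the criterion cannot fail. The words just before it, about each coefficient exceeding zero, do not settle the matter. The NRSs section describes scales running from no pain to worst possible pain, and on such a scale a positive B_i is a worsening. It is also unclear whether the 0.80 applies to each score separately or to all six jointly.

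At stake is the design-stage support for the claim of effectiveness: whether the trial is large enough for its own rule, and how often that rule would declare success with no effect. Posterior estimates and credible intervals stay interpretable either way.

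**Working it through.** **Inputs from the documents.** Power Statement: five effects, one affected; 70% power at 0.10 and nearly 100% at 0.20, level 0.05; 100 data sets per effect size. Hypotheses H1a: six scores, threshold 0.80, flat priors on the effects.

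**Assumptions not in the documents.** Effect estimates are approximately normal with equal standard errors and exchangeable correlation ρ of 0, 0.5 or 0.7. The SDs, intra-cluster correlations and between-score correlations are not given and Figure 3 is not shown, so 70% cannot be derived from scratch. Instead the standard error is set to reproduce it.

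**Step 1: the plan's own figure.** Let δ = effect / SE. The simulated test rejects when the largest |z| exceeds c, where P(max|z| > c) = 0.05 under the null. For five outcomes c = 2.569 / 2.511 / 2.436 (ρ = 0 / 0.5 / 0.7). Power of 70% at 0.10 then needs δ = 3.057 / 2.985 / 2.901, an SE of 0.10/3.057 = 0.033 to 0.10/2.901 = 0.034.

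Check at ρ = 0:
- P(|z| ≤ c) = 0.95^(1/5), so the four unaffected scores all stay inside with probability 0.95^(4/5) = 0.960.
- Power = 1 − 0.960 × Φ(2.569 − 3.057) = 1 − 0.960 × 0.313 = 0.70.
- Doubling δ gives power above 99.9% at 0.20.

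The stated figures are therefore coherent for that test. In the simulation the variance of the cluster effects grows with the square root of the effect. If the whole SE grew that way it would be 1.19 times larger at 0.20, and power there would be 99.5% to 99.7%.

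**Step 2: the rule as printed.** P(|B_i| > 0) = 1 for a continuous posterior, so success is certain with or without an effect.

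**Step 3: repaired rules, six outcomes, same SE.** With a flat prior, the posterior probability of benefit is Φ(z), so PP ≥ 0.80 means z ≥ 0.8416 in the benefit direction.

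| Reading of the rule | Success, one symptom at 0.10 (ρ = 0 / 0.5 / 0.7) | Success with no effect |
|---|---|---|
| Each of six PP ≥ 0.80 | 0.03% / 2.4% / 5.2% | 0.01% / 1.8% / 4.5% |
| Joint PP for all six ≥ 0.80 | 0.0% / 0.9% / 2.9% | 0.0% / 0.5% / 2.1% |
| Any one PP ≥ 0.80 | 99.6% / 98.5% / 98.0% | 73.8% / 52.2% / 43.4% |
| 80% simultaneous bound excludes 0 (two-sided) | 86% / 89% / 91% | 20% by construction |

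Two entries can be checked by hand at ρ = 0:
- The first row cannot exceed the chance that the five unaffected symptoms all pass, 0.2^5 = 0.00032. That cap (5.2% at ρ = 0.7) holds whatever the effect size or SE, so the row is the same at 0.20.
- The no-effect rate for any one symptom is 1 − 0.8^6 = 0.738.

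None of these readings gives 70% power with 5% error.

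**Step 4: smaller differences.** The simulated test with six outcomes instead of five has critical values 2.631 / 2.567 / 2.483 and about 68% power. With 100 data sets, the exact 95% limits are 60.0% to 78.8% around 70/100. They would be 1.6% to 11.3% if 5 of 100 rejected under the null; the actual count is in the missing figure.

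**The case against.** The strongest reply is that the near-zero success rates are not power in the ordinary sense. If five of six effects are truly zero, a rule requiring all six to pass ought to fail. Under the same assumptions, if all six symptoms improve by 0.10, each-of-six PP ≥ 0.80 succeeds 92% to 93% of the time. This is right, and those rows must not be read as showing that the trial cannot succeed. They show only that 70%, obtained with one affected symptom, cannot be the power of such a rule.

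A second reply is that the absolute value points to a two-sided rule, and that the nearest usable version is an 80% simultaneous bound. Power would then be above the stated 70%, but with 20% error. That also stands, and it confirms that the published pair of figures does not carry over.

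Third, the absolute value may be a drafting slip, joint modelling is compatible with a simultaneous test, and the H1a section also mentions credible intervals. All true. But the only acceptance threshold stated is the 0.80 probability, and the intended rule cannot be recovered from the text.

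Fourth, a Bayesian analysis need not control type I error. But the plan itself offers level and power as design support, so they should describe its own rule.

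The five-versus-six difference is minor: it moves power by about two points, well inside simulation error.

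**Conclusion.** The concern holds. The mismatch is textual and depends on no assumed standard error or correlation: the reported power and error rates belong to a five-effect simultaneous-bounds test, and no operating characteristics are given for the H1a rule or for H1b. As printed, the H1a rule is always met.

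The repaired readings span roughly 0% to over 99% success with one symptom affected at 0.10, and roughly 0% to 74% with no effect. These ranges rest on the normal approximation, equal standard errors, correlations of 0 to 0.7 and an SE set to match the stated 70%. They illustrate the spread and do not estimate the trial's true power, which may lie on either side of 70%. The finding does not challenge enrolment or conduct.

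**What to change.** State one non-degenerate decision rule and use it in both the Power Statement and Hypotheses H1a. The simplest choice is to make the simultaneous-bounds test already simulated the H1a criterion. The alternative is to correct the posterior-probability rule: give its direction, say whether it is joint or per score, and state its error rate. Carry the same rule, with a threshold, to H1b and to the cluster-period fallback model.

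Then rerun the simulation with six outcomes under that rule and restate type I error and power for H1a, with H1b power alongside. More data sets would help: at 70% power the simulation standard error is √(0.7 × 0.3/100) = 4.6 points now, against 1.4 points with 1,000. Until this is done, label the present figures as the power of a five-symptom omnibus test.

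The cost is a revised paragraph, a revised Figure 3 and computing time. The computing is not trivial: 1,000 data sets at eight effect sizes is 8,000 fits, against 800 now, of a model the plan itself calls challenging. Restricting the larger runs to effects of 0 and 0.10 would need 2,000 fits. Enrolment does not change, and the stated power may move in either direction.

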E2C2 / 18-007779

Enhanced, EHR-facilitated Cancer Symptom Control (E2C2)
Pragmatic Clinical Trial

NCT03892967

Document Date: 03/04/2025

IRB Minimal Risk Protocol Template

General Study Information

Principal Investigator: [name], MSCE

Study Title: Enhanced, EHR-facilitated Cancer Symptom Control (E2C2) trial

Protocol version number: March 4, 2025 Version 24

Research Question and Aims

Hypothesis: Collaborative care management for control of moderate or worse sleep disturbance, pain, physical function impairment, anxiety, depression, fatigue (SPPADE symptoms), and physical dysfunction among cancer survivors and patients with cancer will improve quality of life, symptom severity, and adherence to cancer treatment, and will also reduce need for acute care.

Aims:

Specific Aim 1. Conduct a cluster randomized pragmatic trial with a stepped wedge design to test the hypothesis that a symptom control-focused E2C2 intervention will significantly reduce SPPADE symptom and physical dysfunction scores; reduce unplanned hospitalizations, emergency department (ED) visits, and intensive care unit (ICU) admissions; improve adherence to cancer therapies; and improve self-reported quality of life.

H1a. SPPADE symptom scores will improve more, relative to prior scores, for patients who have been exposed to the intervention when compared with the improvement of patients that are not exposed.

H1b. Among patients who report moderate or worse symptoms, SPPADE symptom scores will improve more for patients who have been exposed to the intervention when compared with the improvement of patients that are not exposed.

Specific Aim 2. Evaluate the hypothesis that use of a multifaceted, evidence-based implementation strategy to support adoption and use of the E2C2 system will result in improvements in implementation and clinical outcomes.

Specific Aim 3. Conduct a mixed methods evaluation to detect, understand and reduce disparities in the adoption and implementation of the E2C2 intervention among elderly and rural-dwelling patients with cancer.

Background:

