
The primary outcomes of the trial are a bundle of 6 SPPADE symptom and function scores assessed with numerical rating scales (NRSs) collected in association with medical oncology clinic appointments. The primary analysis will test differences in the change in mean joint SPPADE symptom NRS scores in all participants, and in those who experience elevated (4-10/10) symptoms, between participants who are exposed to the intervention and those who are not. Secondary outcomes will include PROMIS-CAT measures for anxiety, depression, pain, and physical function, assessed up to every four months depending on visit frequency. Additional secondary outcomes will include health care utilization, adherence to cancer treatment, and survival. Variation in ePRO response rates and outcomes will be assessed for all participants, but special emphasis will also be given to disparities in outcomes among elderly and rurally based patients.

Process measures will capture stakeholders' use of the EHR graphic and decision support tools and will be abstracted from the EHR. All analyses will be performed using methods appropriate for cluster randomized stepped wedge trials. In parallel with conduct of the E2C2 trial, mixed methods will be used to comprehensively assess system usability, multi-stakeholder experience, and barriers and facilitators for stakeholders' use of the system. Qualitative interviews will also

be conducted to understand possible reasons for disparities in the adoption and implementation of the E2C2 intervention among elderly and rural-dwelling patients with cancer.

Cancer Patient Enrollment: This is a population-based study, where all eligible patients seen by clinicians at the Medical Oncology Clinic in Rochester and hematology/oncology in the Midwest Mayo Clinic Health Systems (MCHS) will be enrolled. This inclusive enrollment approach substantially increases the generalizability and external validity of our real-world pragmatic trial. Rochester campus will act as primary research site and there will be no study team responsibilities at any of the MCHS sites.

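### Modelling the six SPPADE scores jointly does not by itself remove multiplicity, and the H1a decision rule is not the test for which type I error and power are stated

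*Combined protocol and SAP*

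**What the plan says.** The Data Analysis Plan (Specific Aim 1, Hypotheses H1a) fits one multivariate mixed model to the six scores, "which will allow us to account for the correlation between them and avoid correcting for multiple hypothesis tests". The intervention effects B_1 to B_6 are fixed effects. Apart from the priors on calendar time, "All other priors will be flat". At the decision step, "we will achieve the primary aim of the study by calculating the posterior probabilities that each of" B_1 to B_6 is greater than 0. The intervention is accepted as effective if `PP[abs(B_i) > 0, i = 1,…,6] ≥ 0.80`.

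The Power Statement describes something else. It tests the hypothesis that all effects are zero by simultaneous credible bounds. It lists ν_1B to ν_5B, which is five effects rather than six, and covers the case where "only a single symptom is affected by the intervention". For that test it reports type I error close to the nominal 0.01, 0.05 or 0.10, power of 70% at a difference of 0.10 (level 0.05), and nearly 100% at 0.20.

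The design overview (Study Design and Methods) words the contrast in a third way: "The primary analysis will test differences in the change in mean joint SPPADE symptom NRS scores in all participants". The H1b rule repeats the absolute-value form with no threshold, and the cluster-period fallback states no combining rule.

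**The concern.** Putting six outcomes in one model gives the correct joint distribution of the six estimates. It does not change the number of chances to be wrong if each coefficient is then judged by its own posterior probability. With flat priors on fixed effects there is no shrinkage across symptoms to offset this.

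Whether a correction is needed therefore depends on the combining rule, which the plan leaves open. If one symptom is enough, a null intervention has six chances to pass. If all six must pass, no correction is needed, but a benefit confined to one symptom can hardly ever be declared. Either way, the type I error and power in the Power Statement belong to a different test. The trial would go to analysis without a stated error rate or power for its own primary decision.

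**Working it through.** **The plan's own figures.** The 70% and the near-100% cannot be rebuilt from scratch, because the variances, covariance matrices and cluster sizes are not given and Figure 3 is not shown. They can be checked against each other.
- Take six equicorrelated estimates with correlation ρ = 0.5 and simultaneous two-sided 95% bounds. The critical value is 2.57.
- One shifted symptom reaches 70% power at a shift of 3.04 standard errors. A difference of 0.10 then implies a standard error of 0.10 / 3.04 = 0.033.
- If the standard error is the same at 0.20, power there exceeds 99.9%. With five effects the critical value is 2.51, the shift 2.98, and the result the same.

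So the two stated powers are consistent with a simultaneous-bounds test. With 100 data sets per setting, the Monte Carlo standard error is √(0.7 × 0.3 / 100) = 4.6 points at 70% and √(0.05 × 0.95 / 100) = 2.2 points at 5%.

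**Inputs for the stated rule.**
- From H1a: six coefficients, flat priors and the threshold 0.80.
- Assumed: the rule is read in the improving direction, and the six estimates are equicorrelated normals. ρ is not in the documents, so it is varied from 0 to 0.9.

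Under a flat prior, a directional posterior probability of at least 0.80 is approximately a one-sided test at 0.20, so c = 0.842.

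**Formulas.** Write z_i = √ρ·u + √(1−ρ)·e_i, with u and e_i standard normal, and q(u) = Φ((√ρ·u − c)/√(1−ρ)).
- Any one symptom suffices: 1 − ∫φ(u)[1 − q(u)]⁶ du. At ρ = 0 this is 1 − 0.8⁶ = 73.8%.
- All six must pass: ∫φ(u) q(u)⁶ du. At ρ = 0 this is 0.2⁶, about 0.01%.
- Any one, each at two-sided 0.05: 1 − ∫φ(u) r(u)⁶ du, where r(u) is the conditional chance that |z_i| < 1.96. At ρ = 0 this is 1 − 0.95⁶ = 26.5%.
- Single joint posterior probability that all six improve, required to reach 0.80: by simulation.
- All six must pass when one symptom is truly affected by δ standard errors: ∫φ(u) q(u)⁵ q_δ(u) du, where q_δ uses c − δ in place of c.

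**Results.**

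| ρ | Null: any, 0.80 | Null: any, two-sided 0.05 | Null: all six, 0.80 each | Null: joint probability ≥ 0.80 | One symptom affected: all six pass |
|---|---|---|---|---|---|
| 0 | 73.8% | 26.5% | 0.01% | about 0% | 0.03% |
| 0.3 | 60.6% | 24.1% | 0.5% | 0.07% | 0.8% |
| 0.5 | 52.2% | 20.7% | 1.8% | 0.6% | 2.4% |
| 0.7 | 43.4% | 16.4% | 4.5% | 2.3% | 5.2% |
| 0.9 | 32.5% | 10.8% | 10.0% | 7.4% | 10.7% |

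The last column hardly depends on δ. It is 2.4% at ρ = 0.5 both for δ = 3.04 (70% power with simultaneous bounds) and for δ = 1.96 + 0.524 = 2.48 (70% power for one unadjusted test). The limiting factor is that five unaffected symptoms must also pass, which at ρ = 0 has probability 0.2⁵ = 0.03%.

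**Readings of the rule against the simulated test.**
- Any: a union of six unadjusted 0.80 criteria, not simultaneous bounds.
- All six, or the joint probability: an intersection, which is the opposite of a global null rejected by one symptom.
- Literal abs(B_i) > 0: posterior probability 1 for a continuous coefficient, so it is always met.

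None of these is the test in the Power Statement.

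**The case against.** The strongest reply is that an index range inside one probability bracket, following the words each of, ordinarily means all six. Nothing in the H1a text says that any one symptom suffices. On the all-six reading the sentence about avoiding correction is defensible, because requiring every component to pass does not inflate error. This stands: it is the more natural reading, and the 52% belongs to the less natural one. It is also true that much of the 52% comes from the lenient 0.80 threshold, since at two-sided 0.05 each the figure is 20.7%. Finally, the plan presents the single-symptom case as its most conservative one, not as the expected benefit. If all six symptoms shifted by 2.48 standard errors, the all-six rule would succeed about 81% of the time at ρ = 0.5.

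The reply does not rescue the plan, because the all-six reading detaches the rule from the stated power.

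Three stronger inferences are not supported:
- A reader might take 2% to over 50% as the range of the trial's false-positive rate. Those figures hold only near ρ = 0.5 with a directional 0.80 rule, and other readings fall outside them.
- A reader might conclude that the contrast will be picked once the six results are known. No passage says so.
- A reader might count the mean of six scores as a settled third primary contrast. It appears in the design overview. The analysis section drops the word mean, and no such statistic is defined.

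**Conclusion.** The point holds. The statement that joint modelling avoids multiplicity correction is wrong as a general claim and true only under a combining rule that the plan does not state. The H1a rule is also not, on any reading, the test to which the stated error control and 70% power belong. This second part needs no assumption about correlation.

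The sizes are illustrations, not bounds. They rest on equicorrelated normal estimates, flat priors and a directional reading. For ρ from 0 to 0.7, the false-positive rate is 74% to 43% if any symptom suffices at 0.80, and 26.5% to 16% with each symptom at two-sided 0.05. It is 0.01% to 4.5% if all six must pass. In that last case a benefit on one symptom would be declared 0.03% to 5% of the time, against the 70% stated for such an effect at a difference of 0.10.

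**What to change.** Delete the statement that joint modelling avoids correcting for multiple tests. Make the H1a decision rule the test already used in the Power Statement: reject the global null that all six B_i are zero when simultaneous 95% credible bounds from the joint posterior exclude zero, in the improving direction, for at least one symptom. Claim an individual symptom only from its own simultaneous bound. Report all six bounds, so that worsening on any symptom is visible beside a positive global result. Use the same construction for the six H1b coefficients and in the cluster-period fallback. Rerun the type I error and power simulation with six scores under this rule.

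An all-six or mean rule would be equally legitimate. If the sponsor intends one of these, it should be written out and the power restated for it.

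The cost is SAP wording and a repeat simulation, since the bounds come from the same MCMC draws. Per-symptom intervals widen: for ρ from 0 to 0.7 the multiplier is 2.63 to 2.48 instead of 1.96. Counting only the improving direction gives a global false-positive rate of about 2.5%. By the same integrals at ρ = 0.5, it takes power at the 70% point to about 68%.
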